1 SYNOPSIS

Deep vein thrombosis (DVT) is a severe disease which may cause severe disability and which is sometimes fatal. Conventional treatment with low molecular weight heparin (LMWH) and oral anticoagulants is associated with some degree of long-term sequelae, i.e., post-thrombotic syndrome (PTS), in more than 60-80% of the patients. Systemic thrombolytic therapy reduces the risk of PTS, but is associated with an unacceptably high risk of bleeding complications, many being disabling or fatal. Catheter-directed thrombolytic (CDT) therapy is a novel treatment modality which has been introduced in many hospitals worldwide. Low dose fibrinolytic agents are delivered continuously and directly into the thrombus through a catheter until thrombus has dissolved. Although many, mostly small series, have suggested a beneficial effect of this costly treatment in terms of increased patency of the veins and improved short term functional outcome, there are no randomized clinical trials documenting its short and long-term efficacy and safety.

The present study is a randomized, open-label, multi-center clinical trial among hospitals in the Eastern and Southern Norway Health Authorities (Helse Øst and Sør). Patients with acute iliofemoral vein thrombosis will be randomized to either conventional treatment or CDT in addition to conventional treatment. Main outcome parameters are patency rates at 6 months and prevalence of PTS at 24 months. A number of secondary outcomes include bleeding complications, recurrent thrombosis, quality of life (QoL), markers of importance for successful lysis and recurrent thrombosis, and whether PTS is related to patency at the end of treatment.

Our main short-term hypothesis is that CDT of first-time acute DVT will increase patency of the affected iliofemoral vein segments after 6 months from <50% on conventional therapy to >80% after CDT. Our main long-term hypothesis is that CDT will improve long-term functional outcome, i.e., risk of PTS, assessed after 2 years, from >25% on conventional treatment to <10% after CDT. The estimated sample size is at least 100 evaluable patients in each group using a statistical significance (α) = 5% and a statistical power ($1-\beta$) = 80%.

2 BACKGROUND

Deep vein thrombosis (DVT) of the lower extremities is a common disease, which is associated with significant morbidity. The incidence of DVT is estimated as 1 event per 1,000 per year, which ranks it as one of the more common cardiovascular disorders ¹. Furthermore, DVT is associated with several important short- and long-term outcomes ². Short-term there are symptoms of pain and swelling due to inflammation and obstruction. In a small minority of cases, the condition leads to phlegmasia cerulea dolens in which extensive venous obstruction leads to ischemia or infarction of the extremity. Lastly, DVT can also lead to pulmonary embolism (PE), which can be fatal. Long-term sequelae of DVT include recurrent venous thromboembolism (VTE), post-thrombotic syndrome (PTS), and chronic thromboembolic pulmonary hypertension.

Anticoagulation therapy is the basic treatment of DVT³, which purpose is to inhibit the thrombotic process and the inflammatory response so that the thrombus can be cleared by endogenous fibrinolysis. Anticoagulation therapy thereby alleviates acute symptoms, prevents PE, and recurrent events. In most cases, anticoagulation is achieved acutely with unfractionated heparin (UFH) or low molecular weight heparin (LMWH) therapy, followed by long term anticoagulation with oral vitamin K antagonists (eg warfarin).

Anticoagulation therapy is highly efficacious for the prevention of recurrent VTE, PE, and death^{3,4}, but the ability to prevent PTS as an outcome is less clear⁵. PTS is thought to be a result of residual venous stenosis and damage to the venous valves which together cause venous hypertension. Venous hypertension leads to chronic edema and fibrin deposition in the interstitial tissues, which in turn bring about poor oxygen exchange. Insufficient oxygenation induces skin changes, pain and, in severe cases, chronic ulceration.

Tsapogas	4/19	(21)	0/15	(0)	17.0	(0.3, 1022)
Porter	4/24	(17)	1/26	(4)	4.2	(0.5, 34)
Elliot	2/26	(8)	0/25	(0)	9.4	(0.1, 607)
Schulman ²²	3/17	(18)	1/19	(5)	3.3	(0.4, 29.4)
Arnesen	2/21	(10)	2/21	(10)	1.0	(0.1, 7.1)
Total	20/115	(16)	6/124	(5)	3.9	(1.5, 10.3)

Table 2 Summary results for the trials comparing urokinase (UK) to intravenous unfractionated heparin (UFH); Values in parentheses are percent of cases.

Study	UK Events/N (%)	UFH Events/N (%)	Odds Ratio (95% CI)
Efficacy = significant lysis			
Goldhaber ²³	1/8 (13)	1/9 (11)	1.1 (0.1, 2.9)
Kiil ²⁴	1/11 (9)	1/9 (11)	0.8 (0, 14.9)
Total	2/19 (11)	2/18 (11)	1.0 (0.1, 7.2)
Major Hemorrhage			
Goldhaber	0/8 (0)	1/9 (11)	0.2 (0, 16.3)
Kiil	0/11 (0)	3/9 (33)	0.8 (0, 2.8)
Total	0/19 (0)	4/18 (22)	

Table 3 Summary results for the trials comparing recombinant tissue plasminogen activator (rt-PA) to intravenous unfractionated heparin (UFH); Values in parentheses are percent of cases.

Study	rt-PA Events/N (%)	UFH Events/N (%)	Odds Ratio (95% CI)
Efficacy = significant lysis			
Goldhaber ²³	15/53 (28)	0/12 (0)	10.1 (0.8, 999)
Turpie 2 ²⁵	6/29 (21)	2/30 (7)	3.7 (0.6, 29)
Turpie 1 ²⁵	7/12 (58)	0/12 (0)	34.1 (2.0, 999)
Total	28/94 (30)	2/54 (4)	11.7 (2.6, 53)
Major Hemorrhage			
Goldhaber	1/53 (2)	0/12 (0)	0.7 (0.01, 999)
Turpie 2	0/29 (0)	0/30 (0)	0.3 (0, 22000)
Turpie 1	1/12 (0)	0/12 (0)	1.0 (0.02, 43)
Verhaeghe ²⁶	0/11 (0)	3/9 (33)	7.3 (0, 2.8)
Total	0/105 (2)	3/63 (48)	0.4

documentation of its efficacy and high short-term risk of bleeding²⁷. Overall only a few hundred patients have been evaluated in randomized clinical trials. The effects of SK treatment versus heparin are summarized in Table I, the effects of urokinase versus heparin in Table II, and that of rt-PA versus heparin in Table III. The overall clinical effects are shown in Table IV.

Table 4 Summary results of all trials of thrombolytic therapy for acute DVT (after¹³).

Treatment	Success rate (% with significant lysis)	Major hemorrhage (%)
Unfractionated heparin	12	6
SK	62	16
SK high dose	Uninterpretable	Uninterpretable
SK low dose	27	15
UK	11	0
rt-PA	30	8
rt-PA high dose	6	29
rt-PA local administration	27	10
Catheter directed (UK and rt-PA) (no randomized clinical trials)	83	11

Several published studies using ultrasound imaging have demonstrated considerable endogenous ability to lyse thrombi after conventional anticoagulation therapy². One year after acute DVT, somewhere between 30% and 73% of patients will normalize their ultrasound findings. Earlier in the disease course, patency rates are lower, demonstrating that over time there is continued recanalization of the vein. The studies do not describe PTS incidence and whether or not development of the condition correlates with recanalization status. Without this information, it is difficult to answer the important question of whether or not early recanalization protects against development of PTS.

Catheter-directed thrombolytic therapy (CDT) is a relatively new technique for treatment of DVT^{13;28} and its efficacy has recently been reviewed²⁹. It involves application of the thrombolytic agent directly into the thrombus using a catheter with multiple side holes. The catheter is passed into the clot under radiographic guidance. The venous puncture may be central or peripheral to the thrombosed vein. For thrombolysis of the pelvic and the femoral veins, the access was in the early studies of the internal jugular, or the contralateral or ipsilateral femoral veins. Subsequent investigators have used the ipsilateral popliteal vein with success and this appears to be the site of choice. The thrombolytic agent is administered over 1-4 days until dissolution of the clot is apparent. Both UK, alteplase (Actilyse®), reteplase (Rapilysin®) and tenecteplase (Metalyse®) has been used, but UK is no longer available in the market, and only alteplase may be given as a continuous iv infusion, preferably at 0.001-0.02 mg/kg/hour^{30;31}. Heparin therapy should be given concomitantly intravenously probably at subtherapeutic doses^{29;30;32;33}, corresponding to a 1.2-1.7 times prolongation of aPTT.

The decision to discontinue the drug is based on daily venographic examinations through the indwelling catheter. Depending on the findings the catheter may be pulled out, the infusion continued, or the catheter repositioned. To obtain flow in the veins balloon inflation may be performed at the follow-up. Thrombolytic agents are given until there is no more evidence of thrombosis or until there is little improvement in venographic appearance. After 72-96 hours thrombolysis is discontinued. Adjuvant therapies include angioplasty, angioplasty with stents, thrombectomy, and surgically created arterio-venous fistulas.

So far, there are no randomized clinical trials with long-term follow-up on the efficacy of CDT therapy, but at least 15 case series have been reported^{29;34-37}. Combining the studies, 263 patients received this type of therapy for thrombosis of the iliofemoral veins or inferior vena cava. 221 (84%) patients were considered to have successful short-term outcomes based on venographic appearance and 13 (4.9%) patients had bleeding severe enough to warrant transfusion. Long term outcomes were not reported, and the authors did not describe the proportion of patients requiring adjuvant therapy.

A National DVT Registry was established in North-America to analyze results in a large number of patients treated with CDT³⁸. This registry included 473 patients with documented lower extremity DVT treated with CDT, but follow-up data included only 287 patients who received 312 treatments. Thrombi subjected to lysis included either ilio-femoral vein thrombosis in 71% of cases and femoro-popliteal vein thrombosis in 25% of cases. The mean age of patients was 47.5 years and the mean duration of infusion was 53 h. All patients had six months of therapy with oral anticoagulants following CDT and many had heparin as well. Complete lysis was obtained in 31% of patients, 50-99% lysis in 52% and <50% lysis in 17%. Successful lysis was not related to location of the thrombus. The overall primary patency rate was 80% at 12 months, with better patency for ilio-femoral segments than the femoro-popliteal segments. Major bleeding complications occurred in 11% of patients; 39% of these at the venous insertion site, 13% were retroperitoneal hematoma. Minor bleeding events occurred in 16% of patients, again most often at the venous entry site. There was one fatal intracranial hemorrhage, one subdural hematoma, and 6 pulmonary emboli of which one was fatal. Thus, the overall mortality rate from lysis was 0.4%. There was no data on PTS.

If the PTS differs between standard therapy and thrombolytic therapy then the quality of life may differ between patients also. Comerota assessed health-related quality of life in patients after CDT therapy compared to a group of patients treated with standard anticoagulation therapy³⁹. The delayed functional outcome and wellbeing scores were significantly better in the thrombolytic therapy group. Although this study had some methodological shortcomings¹³, the findings are still suggestive that thrombolytic therapy may offer improved quality of life in patients who achieve successful thrombolysis.

Compared to historical data of anticoagulation and intravenous thrombolysis, CDT probably has higher recanalization rates. The studies so far, including one RCT with 6 months follow-up and 35 patients⁴⁰, have been promising, but unfortunately no high-quality randomized studies with long-term follow-up have been performed. Experimental data indicate that valves of the femoral veins may be preserved^{41;42}. It is therefore possible that PTS may be reduced. However, long term studies have not been performed. In the absence of well-designed randomized clinical studies both for early findings, the implications of early patency for long-term clinical results, the complications, and the costs related to treatment, CDT therapy for DVT should at present be considered experimental treatment. Still, some Norwegian hospitals including Aker and Ullevål University Hospitals, Rikshospitalet, and the Østfold Hospital Trust Fredrikstad, do provide this high-intensive treatment to selected patients. A case-series with careful follow-up at Aker University Hospital has recently been published³¹.

In the present study, we aim to investigate the role of CDT therapy for treatment of acute DVT as compared with established treatment with low molecular weight heparin. The study will be an open-label, randomized study of patients with first-time acute DVT of the affected limb, and our major outcome parameter will be the frequency of PTS as related to early venographic patency. The results of this study have the potential to properly define the role of this costly treatment in the future.

3 OBJECTIVES

3.1 PRIMARY OBJECTIVES

To investigate whether catheter-directed thrombolytic therapy for first-time acute DVT of the iliofemoral veins may:

- 3.1.1 increase patency rate at 6 months.
- 3.1.2 reduce the risk of PTS at 2 years.

3.2 SECONDARY OBJECTIVES

- 3.2.1 To investigate frequency of clinically relevant bleeding related to the procedure.
- 3.2.2 To investigate effects on quality of life (QoL).
- 3.2.3 To investigate cost-effectiveness of treatment.
- 3.2.4 To investigate the procedural success of CDT.
- 3.2.5 To identify markers of importance for successful thrombolysis.
- 3.2.6 To investigate patency at 2 years.
- 3.2.7 To investigate PTS at 6 and 60 months.
- 3.2.8 To investigate whether presence or absence of PTS at any time point is related to patency at end of treatment.
- 3.2.9 To investigate prevalence of vein anomalies (and need for angioplasty or stents).
- 3.2.10 To investigate prevalence of underlying thrombophilia.
- 3.2.11 To investigate frequency of recurrent VTE during follow-up.
- 3.2.12 To identify markers of importance for recurrent thrombosis.

4 HYPOTHESES

Our main short-term hypothesis is that CDT of first-time acute DVT will increase patency of the affected iliofemoral vein segments after 6 months from <50% on conventional therapy to >80% after CDT. Our main long-term hypothesis is that CDT will improve long-term functional outcome, i.e., risk of PTS, assessed after 2 years, from >25% on conventional treatment to <10% after CDT.

5 PATIENT POPULATION

5.1 INCLUSION CRITERIA

- 5.1.1 Age 18-75 years.
- 5.1.2 Onset of symptoms <21 days.
- 5.1.3 Objectively verified DVT (ultrasonography, venography, computed tomography, or magnetic resonance imaging) localized in the upper half of the thigh, the common iliac vein or the combined iliofemoral segment.
- 5.1.4 Informed consent (Appendix 1).

5.2 EXCLUSION CRITERIA

- 5.2.1 Anticoagulant therapy prior to trial entry for >7 days.
- 5.2.2 Contraindications to thrombolytic therapy, including bleeding diathesis.
- 5.2.3 Indications for thrombolytic therapy, e.g., phlegmacia coerulea dolens or isolated vena cava thrombosis.
- 5.2.4 Severe anemia (hemoglobin <8 g/dL).
- 5.2.5 Thrombocytopenia (platelets <80·10⁹/L).
- 5.2.6 Severe renal failure – creatinine clearance <30 ml/min. Creatinine clearance will be calculated according to the following formula:

$$\text{Creatinine clearance (ml/min)} = \frac{b \times (140 - \text{age (yrs)}) \times \text{body weight (kg)}}{\text{serum creatinine } (\mu\text{mol/L})}$$

$$b=1.23 \text{ (females); } 1.04 \text{ (males)}$$

- 5.2.7 Severe hypertension, i.e. persistent systolic blood pressure >160 mm Hg or diastolic blood pressure >100 mm Hg.
- 5.2.8 Pregnancy and thrombosis ≤7 days post-partum (may be included after 7 days post-partum).
- 5.2.9 Less than 14 days post-surgery or post-trauma (may be included after 14 days).
- 5.2.10 History of subarachnoidal or intracerebral bleeding.
- 5.2.11 Disease with life expectancy <24 months.
- 5.2.12 Drug abuse or mental disease that may interfere with treatment and follow-up.
- 5.2.13 Former ipsilateral proximal DVT.
- 5.2.14 Malignant disease requiring chemotherapy.
- 5.2.15 Any thrombolytic therapy within 7 days prior to trial inclusion.

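### The sex constants in the creatinine-clearance formula (Protocol 5.2.6) are transposed, so women at about 25.4 to <30 ml/min pass the renal exclusion and men at 30 to <35.5 ml/min are wrongly excluded

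*Protocol*

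**What the plan says.** The exclusion in Protocol section 5.2.6 reads "Severe renal failure – creatinine clearance <30 ml/min". The method is prescribed: "Creatinine clearance will be calculated according to the following formula". The numerator is "b \times (140 - \text{age (yrs)}) \times \text{body weight (kg"), the denominator is "serum creatinine } (\mu\text{mol/L"), and the sex constant is "b=1.23 \text{ (females); } 1.04 \text{ (males").

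The formula appears nowhere else in the protocol. Its source is neither named nor cited, and no other section corrects the labels. The eligible age range in section 5.1.1 is "Age 18-75 years".

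**The concern.** A constant multiplied by 140 minus age and by weight, divided by serum creatinine, is the Cockcroft-Gault estimate of creatinine clearance. Its sex factor lowers the estimate in women, who generate less creatinine per kilogram. The printed version does the reverse: at equal age, weight and creatinine, a woman receives the higher clearance.

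This is an operative eligibility rule. Both arms receive low molecular weight heparin dosed by weight, and the CDT arm also receives rt-PA with unfractionated heparin (sections 6.4.2 and 6.4.3). The protocol does not say why it excludes severe renal failure, but protection against bleeding is a reasonable reading. If sites follow the text, some women whom the limit is meant to keep out can be randomized, and some men whom it is meant to admit are refused.

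There is also a link to the analysis. Section 8.2 allows patients who were ineligible and included by mistake to be removed after randomization. For renal function, this formula decides who was ineligible.

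**Working it through.** **Inputs**

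- From section 5.2.6: b = 1.23 (females) and 1.04 (males), creatinine in µmol/L, exclusion below 30 ml/min.
- From section 5.1.1: age 18 to 75, which bounds the examples.
- Not in the protocol, but general technical knowledge: the standard equation is (140 − age) × weight / (72 × creatinine in mg/dL), multiplied by 0.85 for women, and 1 mg/dL of creatinine is 88.4 µmol/L.

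**Step 1: reproduce the constants.**

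- Men: 88.4/72 = 1.228, which rounds to 1.23.
- Women: 1.228 × 0.85 = 1.044, which rounds to 1.04.

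Both printed values reproduce to two decimals, each against the opposite sex. No choice of unit or rounding gives women the larger constant.

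**Step 2: size of the error.**

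- Women: 1.23/1.04 = 1.183, so clearance is overstated by 18.3%.
- Men: 1.04/1.23 = 0.846, so clearance is understated by 15.4%.

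**Step 3: who is misclassified at 30 ml/min.**

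- Women score 30 or more as printed once their correct value reaches 30 × 1.04/1.23 = 25.4. Those at 25.4 to <30 pass when they should be excluded. Those below 25.4 are still excluded.
- Men score below 30 as printed until their correct value reaches 30 × 1.23/1.04 = 35.5. Those at 30 to <35.5 are excluded when they should pass.

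**Step 4: worked patients (ml/min).**

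| Patient | As printed | Labels swapped |
|---|---|---|
| Woman, 70 y, 60 kg, 160 µmol/L | 1.23 × 70 × 60/160 = 32.3 (passes) | 1.04 × 70 × 60/160 = 27.3 (excluded) |
| Man, 70 y, 80 kg, 200 µmol/L | 1.04 × 70 × 80/200 = 29.1 (excluded) | 1.23 × 70 × 80/200 = 34.4 (passes) |

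**Step 5: the same shift on the creatinine scale.** Exclusion starts when creatinine exceeds b × (140 − age) × weight/30.

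- Woman, 70 y, 65 kg: 1.04 × 70 × 65/30 = 158 µmol/L with the correct constant, and 1.23 × 70 × 65/30 = 187 as printed.
- Man, 70 y, 80 kg: 1.23 × 70 × 80/30 = 230 µmol/L with the correct constant, and 1.04 × 70 × 80/30 = 194 as printed.

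**The case against.** The protocol does not contradict itself here. It never names the equation, and the 72, the 0.85 and the 88.4 all come from outside it. That is true and should be said openly. It does not rescue the text, because the algebra, the units and both constants identify the equation, and anyone can check the conversion. The point does not depend on recalling a particular study's result.

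The effect is also confined to two bands. The renal exclusion does not fail for women generally, only between about 25.4 and 30 ml/min, and the error in men costs recruitment and not safety. No distribution of renal function is given, so the number affected could be none or some unknown share of the roughly 200 planned patients (section 8.1). The separate exclusion for contraindications to thrombolysis (section 5.2.2) might catch some of these women, but the protocol does not allow that to be judged. Sites may also have used their own calculators with the correct constants. All of this limits the practical reach, and it stands.

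Finally, eligibility is settled before randomization and applies to both arms, so the treatment comparison is not biased and sample size is unaffected. That stands too. The case for correction rests on a safety-related criterion being wrong as written. A fault in reading the PDF is unlikely, since both labels are complete and legible; a look at the original page would settle it.

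**Conclusion.** The concern holds. The two sex labels in section 5.2.6 are transposed, and the rule gives wrong eligibility decisions in the two bands shown above: it is too lenient for women and too strict for men. The conclusion assumes only that the formula is the standard equation its form and constants match. The limit of 30 ml/min is not in question. How many patients are affected cannot be estimated from the protocol, and there is no effect on power, type I error or the validity of the randomized comparison. It should still be corrected without fail, because it is an operative rule that sites are told to apply and the correction is almost free.

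**What to change.** Amend section 5.2.6 so that b is 1.04 for females and 1.23 for males, and leave the limit unchanged. Naming the equation there would let sites verify it.

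If a case report form, worksheet or site calculator took its constants from the protocol, correct that as well. If patients have already been screened with the printed constants, recompute their clearance and list any whose eligibility changes.

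State in the amendment how patients randomized under the printed rule are treated in relation to section 8.2. They met the criteria then in force, so the recomputation should not become a reason to drop them from the intention-to-treat analysis.

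The cost is a one-line amendment, a notice to sites and, where needed, a recalculation from data already collected. Sample size and timelines do not change.

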6 METHODS

6.1 DESIGN

Multi-center, open-label, randomized clinical study on the effect and safety of CDT therapy as compared with conventional therapy for the treatment of acute, first-time ilio-femoral DVT. The study will be a collaborative study of hospitals belonging to the Eastern and Southern Norway Health Authorities (Helse Øst and Sør).

6.2 PATIENT RECRUITMENT

Eligible patients (section 5) will be invited to participate in the study. Informed consent (Appendix 1) in accordance with the revised Helsinki Declaration must be obtained from the patient before randomization.

6.3 RANDOMIZATION

Patients will be randomized by sealed numbered envelopes using block randomization. Each envelope will contain information on treatment allocation. A new patient will be allocated the lowest numbered envelope. Treatment will be open-label, but stratified for extension of DVT, i.e., only femoral or iliofemoral DVT.

